Statistical Plan, Results and Conclusions for:

A Clinical Decision Support Tool for Electronic Health Records (Official Title)

NCT number 02697643

Document Date: August 9, 2018

Analytic Approach.

Primary Analytic Approach. We are interested in learning whether participants in the intervention condition, BH-CDS, as compared to the control condition, treatment as usual, have (1) greater access to wraparound services, (2) more treatment visits, and (3) longer retention in treatment. As secondary hypotheses, we will examine whether the intervention condition, as compared to the control condition, will be associated with significantly (1) greater psychosocial outcomes, and (2) reduced drug use. A mixed model analytic approach was chosen for its ability to: adjust for individual-level covariates; take into account nesting of clients within counselors; and efficiently maximize the correlated nature of the repeated measures data in the design. Each mixed model will include fixed effects (condition, time and condition-by-time); random effects (clients nested within counselors); repeated measures variation (time); as well as potential counselor-level demographic covariates (e.g., experience level) and client-level demographic covariates (i.e., age). Non-significant covariates will be removed systematically. After arriving at the final model for each analysis, the condition-by-time effect will be examined for significance. In the presence of a significant condition-by-time effect, Bonferroni corrected post-hoc contrasts will be conducted to test for differences between conditions on mean change from baseline to one month follow-up and baseline to three month follow up

Analyses by Hypothesis

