Primary Hypothesis 1: Clients in the experimental condition will have significantly greater matched evidenced-based and wraparound services than clients in the control condition. To address this hypothesis, a chart review was conducted to enumerate services received during the study period. The percentage of services that clients in the experimental condition received from the list of tailored recommendations was calculated. We then compared this percentage to the percentage of services that clients in the control condition would have received had they been in the experimental condition and received tailored recommendations. Because all clients participating in the study completed the PDE, we were able to determine which set of recommendations clients in the control condition would had received had they been in the experimental.

Primary Hypothesis 2: Clients in the experimental condition will have greater engagement in treatment than clients in the control condition. Engagement in treatment was calculated by dividing the number of treatment sessions attended during the study period by the total number of scheduled treatment sessions (i.e., opportunities for treatment), a sum of treatment sessions attended plus the number of scheduled sessions that the client did not show up for (no-show). An independent samples T-test was utilized to determine whether there were statistically significant differences between participants in the experimental and control groups with respect to treatment engagement.

Primary Hypothesis 3: Clients in the experimental condition will have less frequent use of substances than clients in the control condition. Use of substances was measured by the number of relapses during the study period. An independent samples *T*-test was conducted to evaluate whether participants number of relapses differed significantly between the experimental and control groups.

Primary Hypothesis 4: Clients in the experimental condition will have greater biopsychosocial functioning than clients in the control condition. Biopsychosocial functioning was captured by the seven ASI-MV composite scores. The ASI-MV was administered at baseline, 1-month follow-up and 3-month follow-up. Change in the ASI-MV composite scores was evaluated over time and across participant groups with a repeated measures mixed model.

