Primary Hypothesis 1: Clients in the experimental condition will have significantly greater matched evidenced-based and wraparound services than clients in the control condition. Results test indicated no significant difference for experimental and control groups.

Primary Hypothesis 2: Clients in the experimental condition will have greater engagement in treatment than clients in the control condition. T-tests indicated that the experimental and control groups did not differ with respect to treatment engagement.

Primary Hypothesis 3: Clients in the experimental condition will have less frequent use of substances than clients in the control condition. The mean number of relapses during the study period for the experimental group was not significantly different from the control group.

Primary Hypothesis 4: Clients in the experimental condition will have greater biopsychosocial functioning than clients in the control condition. Results for psychiatric status, medical status, alcohol use, family status, or drug use were not significant. Employment status results suggest that participants in the experimental, CDS, condition had significantly fewer legal problems than controls.

Primary Hypothesis 5: Clients in the experimental condition will have greater cost effectiveness than clients in the control condition. The CDS program did not yield significantly different costs effectiveness than the control group.

Primary Hypothesis 6: Counselors in the experimental condition will report satisfaction with the BH-CDS Program. Overall, counselors found it easy to complete the CDS program and reported that their clients' reaction was "neutral" or "positive" (no counselors reported a negative client reaction).

Counselors exposed to the tailored recommendations, reported that they were easy to understand, easy to integrate into the client's treatment plan, and useful for informing treatment decisions and were more likely to incorporate the tailored recommendations into future treatment planning.

Conclusion

Although the use of clinical decision support is promising, the present effort was unable to empirically demonstrate a direct impact on outcome, retention, amount of service delivered or cost. Further research on the impact of clinical decision support for substance use treatment is warranted.

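### The only significant between-group result (Hypothesis 4) names two domains, so it cannot be assigned to either, and one of the seven ASI-MV composites has no readable result

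*SAP*

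**What the plan says.** **Outcomes.** Under Analyses by Hypothesis, Primary Hypothesis 4, the SAP states: "Biopsychosocial functioning was captured by the seven ASI-MV composite scores". They are measured at baseline, one month and three months and analysed with a repeated measures mixed model. The seven are not listed by name.

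**Test.** Under Primary Analytic Approach: "After arriving at the final model for each analysis, the condition-by-time effect will be examined for significance". If that effect is significant, "Bonferroni corrected post-hoc contrasts will be conducted to test for differences between conditions on mean change from baseline to one month follow-up", and likewise to three months.

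**Status.** Primary Analytic Approach introduces psychosocial outcomes and drug use with "As secondary hypotheses, we will examine whether the intervention condition", and the items that follow are "1) greater psychosocial outcomes, and (2) reduced drug use". Analyses by Hypothesis gives the matching item a different status: "Primary Hypothesis 4: Clients in the experimental condition will have greater biopsychosocial functioning than clients in the control condition".

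**Results.** Under Results, Primary Hypothesis 4: "Results for psychiatric status, medical status, alcohol use, family status, or drug use were not significant". The next and last sentence is: "Employment status results suggest that participants in the experimental, CDS, condition had significantly fewer legal problems than controls". No p-value, estimate or table accompanies either sentence. The Conclusion reports that no direct effect on outcome could be shown.

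**The concern.** A result introduced as employment and stated as legal problems contradicts itself. It cannot be passed over as a slip, because correcting either label leaves the other domain unreported. Hypotheses 1, 2, 3 and 5 are reported without significant differences, and Hypothesis 6 was analysed descriptively. This sentence is therefore the only significant between-group finding in the document. Anyone citing the trial for a benefit in a specific domain would have to guess which one.

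The sentence also does not say whether it reports the condition-by-time effect or a follow-up contrast. Finally, it is one positive among seven composites, and the document states no adjustment across them. That bears on whether the word significant can be kept once the domain is known.

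**Working it through.** **1. Count of results against outcomes**

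| Source | Content | Count |
|---|---|---|
| Analyses by Hypothesis, Primary Hypothesis 4 | composites evaluated | 7 |
| Results, Primary Hypothesis 4, first sentence | psychiatric, medical, alcohol, family, drug: not significant | 5 results |
| Results, Primary Hypothesis 4, second sentence | subject employment, finding legal problems | 1 result, 2 domain names |

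Domain names: 5 + 2 = 7, which matches the stated number. Results: 5 + 1 = 6, so one composite is left without a result. Two repairs of the sentence are possible:

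- Legal was significant: the subject is wrong and employment is unreported.
- Employment was significant: the finding is wrong and legal is unreported.

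Nothing in the document decides between them. That employment and legal are the remaining two composites is inferred from the count, since the seven are not listed.

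**2. Scope of the stated correction**

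The Bonferroni step is described only for the two change-from-baseline contrasts that follow a significant condition-by-time effect within a model. No correction is described for the seven condition-by-time tests taken together.

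**3. Size of the multiplicity point**

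The document gives no alpha, p-value or correlation, so it has no figure to reproduce. Assumption: two-sided 0.05 per composite, no true effect on any of the seven.

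- Independent composites: 1 − 0.95^7 = 0.302.
- Common correlation 0.2, 0.5 or 0.7 (equicorrelated normal statistics): 0.287, 0.230, 0.178.
- Other alphas, independent: 1 − 0.99^7 = 0.068 at 0.01; 1 − 0.90^7 = 0.522 at 0.10.

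The next case credits the full planned sequence: a 2-df condition-by-time test at 0.05, then at least one of two contrasts at 0.05/2 = 0.025, with the contrasts assumed correlated 0.5. Simulation gives 0.036 per composite. Across seven:

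| Correlation between composites | At least one false positive |
|---|---|
| 0 | 0.225 |
| 0.2 | 0.217 |
| 0.5 | 0.178 |
| 0.7 | 0.139 |

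With independent composites, changing the contrast correlation to 0.3 or 0.7 gives 0.236 or 0.205.

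First Holm step for a single significant domain among seven: 0.05/7 = 0.0071. With no p-value given, whether the result would pass cannot be computed.

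**The case against.** **Silence is not evidence.** A reader might infer that the result was not adjusted across the composites. The document does not support that as fact: it gives no Bonferroni divisor and no account of what was done beyond its text. The two-contrast reading is the natural one, but the supportable statement is that no adjustment across the seven is stated. This objection stands.

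**The 30% overstates the risk of this particular claim.** Hypothesis 4 is directional and the reported result favours the experimental arm. Counting only false positives in that direction, a single test per composite gives 1 − 0.975^7 = 0.162 if independent. The two-step sequence gives about 12% if independent and 7% at correlation 0.7. The two-sided figures are the conventional ones, but the smaller figures are a fair measure of a spurious favourable finding. None of them bears on the label contradiction.

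**Holm on a family of seven is premature.** The right family depends on whether Hypothesis 4 is primary or secondary, and the document gives both. This stands, so that status must be settled first.

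**No claim of efficacy depends on the result.** A reader might infer that the Conclusion is wrong because it omits a positive finding, or that the trial claims a benefit on unadjusted evidence. Neither is supported. The Conclusion is null, and mentioning one nominal domain there is optional.

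**The test is partly identified.** The mixed model and the condition-by-time effect are named. What remains open is whether the sentence reports that effect or a contrast, which is minor and is settled when the sentence is corrected.

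None of these objections removes the two labels or the missing seventh result.

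**Conclusion.** The point holds, centred on the mislabelled result. Seven composites are evaluated, six results are given, and the one significant between-group result in the document names two domains. This must be fixed, and the finding needs no assumption beyond the inference that employment and legal are the remaining two composites.

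Multiplicity is secondary. It rests on an assumed two-sided 0.05 and on assumed correlations: about 30% falling to 18% for one test per composite, and about 22% falling to 14% if a corrected contrast was also passed. It affects only whether the one domain may be called significant.

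A reader might go further and conclude that legal is the true finding and a poor employment result was left out, or that the finding is a false positive. The document supports neither: it does not show which label is wrong, and it gives no p-value.

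**What to change.** 1. From the analysis output, correct the sentence to the domain that was actually significant, and state whether it reports the condition-by-time effect or a post-hoc contrast.
2. Report the result for both employment and legal, preferably in a seven-row table with the condition-by-time p-value for each composite.
3. Reconcile Primary Analytic Approach, where psychosocial outcomes are secondary, with the Primary heading of Hypothesis 4, by stating the prespecified status. Do this before choosing any adjustment.
4. Then either label the domain result nominal and exploratory, or call it significant only if it passes Holm across the seven condition-by-time p-values (p < 0.0071 at 0.05). Disclose that Holm was added after results were known.
5. The null Conclusion may stay as it is.

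Cost: wording changes and a short table. If the p-values were kept, nothing is rerun. If they were not, the seven planned models are run once more on existing data. The downside is that the one nominally significant result may no longer be claimable, and an adjustment added after results are known is weaker than a prespecified one.

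### The Conclusion denies any demonstrated impact on outcome, yet the H4 results report one significant difference favouring the experimental arm, on a composite the text does not identify

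*SAP*

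**What the plan says.** Under Analyses by Hypothesis, H4 is a global statement: "Clients in the experimental condition will have greater biopsychosocial functioning than clients in the control condition". It is measured on several endpoints: "Biopsychosocial functioning was captured by the seven ASI-MV composite scores". The method given there is that "Change in the ASI-MV composite scores was evaluated over time and across participant groups with a repeated measures mixed model".

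The Analytic Approach section makes the condition-by-time effect the test to be examined in each mixed model. If it is significant, "Bonferroni corrected post-hoc contrasts will be conducted to test for differences between conditions on mean change" from baseline to one month and from baseline to three months.

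The Results for H4 consist of two sentences. The first is "Results for psychiatric status, medical status, alcohol use, family status, or drug use were not significant". The second is "Employment status results suggest that participants in the experimental, CDS, condition had significantly fewer legal problems than controls".

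The Conclusion then says that "the present effort was unable to empirically demonstrate a direct impact on outcome, retention, amount of service delivered or cost". It does not refer to the significant H4 finding.

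**The concern.** H4 is an outcome hypothesis; the Analytic Approach itself calls the psychosocial measures outcomes. Its results contain one difference described as significant and favourable to the experimental arm. A Conclusion that denies any demonstrated impact on outcome, with no exception or explanation, does not fit that. A reader can quote either sentence accurately and describe the trial differently.

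The significant sentence is itself defective. It opens with employment status and ends with legal problems, which are different domains. Until that is resolved, nobody can say which composite the result belongs to or what was found for the other.

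The reading of the cost analysis also depends on this. The text for Primary Hypothesis 5 interprets the cost comparison according to whether one group had superior outcomes, so it needs a settled answer on outcome.

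**Working it through.** The document gives no estimate, p-value, alpha level or effect size for H4, so there is no figure to reproduce. The check is a comparison of texts, with one calculation for context.

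**1. Count of composites.**
- Planned (Analyses by Hypothesis, H4): 7.
- Reported as not significant (Results, H4): psychiatric, medical, alcohol, family and drug, which is 5.
- Remaining: 7 − 5 = 2. The only two other domains named are employment and legal, and both appear in the single sentence reporting significance.
- So one sentence with one result stands for two composites. One of them is presumably significant and the other has no clear result. The text does not say which is which.

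**2. Results against Conclusion.**
- Results, H4: one significant difference, favouring the experimental arm.
- Conclusion: no demonstrated impact on outcome, unqualified.
- Any rule that lets the second follow from the first would have to be a success criterion for H4 or a multiplicity adjustment across the composites. The H4 text says nothing on how many composites must be significant. The Bonferroni correction in the Analytic Approach applies to the post-hoc contrasts that follow a significant condition-by-time effect. Nothing is stated across the seven composites.

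**3. How easily one of seven arises by chance.** Alpha is not stated in the document, so the values below are assumptions. With seven independent tests and no true effect, P(at least one significant) = 1 − (1 − alpha)^7. With perfectly correlated tests it equals alpha.

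| Assumed alpha per composite | Independent | Perfectly correlated |
|---|---|---|
| 0.05 | 1 − 0.95^7 = 0.302 | 0.05 |
| 0.01 | 1 − 0.99^7 = 0.068 | 0.01 |

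The seven composites come from the same clients and instrument, so the true figure probably lies between the two columns. A Bonferroni threshold across seven at overall alpha 0.05 would be 0.05/7 = 0.0071. Without a p-value, a reader cannot tell whether the reported result would pass it.

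**4. Form of the reported result.** The plan tests condition-by-time and then change to each follow-up. The H4 sentence gives no visit, no change from baseline and no interaction result, so it cannot be matched to the planned test from the text alone.

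**The case against.** The strongest reply is that the Conclusion is a fair summary of the whole study. H4 is global, the Results never declare it supported, five domains are null, and one unadjusted significant composite of seven can coexist with an overall null conclusion. The chance calculation supports such caution, and the Conclusion errs in the conservative direction.

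Much of this stands. A reader might infer that the document gives two opposite answers to H4. It does not: one significant component is not a declaration that H4 was met, and the Conclusion does not name H4. What the reply cannot supply is the reason. Setting the result aside may be right, but the rule that would justify it is the reader's inference and is not written in the document.

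Two further readings go beyond the text.

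- One might say that the plan lets a claim rest only on the corrected contrasts. The Analytic Approach says they will be done after a significant condition-by-time effect; it does not say that no other claim is allowed.
- One might say that the significant result came from an overall condition difference that includes the baseline visit. The document does not say which test produced it, and a short results sentence that names no visit does not show that a different test was used. The H1 to H5 results give no estimates or p-values either.

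**Conclusion.** The point holds as a reporting inconsistency with a missing decision rule. The unqualified Conclusion does not fit the one significant H4 result, the composite behind that result is unidentified, and no stated criterion explains its omission.

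The extent is one of seven composites significant and one of seven without a clear result. That decides whether the public answer on outcome is none, or a difference in one domain. Whether the result is more than chance cannot be judged from the document. The 30% figure rests on an assumed alpha of 0.05 and independence, and falls to 5% under perfect correlation.

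The documents do not establish that H4 was met, that the Conclusion is wrong, or that the wrong test was run. The correction should be made, and it is cheap.

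**What to change.** 1. From the model output, identify which composite was significant, and state the result for employment and for legal status separately.
2. For the significant composite, report the condition-by-time test and the two Bonferroni-corrected change contrasts (baseline to one month, baseline to three months) set out in the Analytic Approach.
3. State whether the result survives adjustment across the seven composites, for example against 0.05/7 = 0.0071. Since no such rule was stated in advance, say that the adjustment was chosen after the results were known.
4. Then correct the text according to what is found:
   - **Interaction significant, and at least one corrected contrast significant:** qualify the Conclusion to say that no impact was demonstrated except a difference on one of seven ASI-MV composites. Name the composite and the visit, and say whether the result is adjusted for seven.
   - **Interaction not significant:** change the H4 sentence to say that the result was not significant under the planned test, and keep the Conclusion.
   - **Interaction significant, neither corrected contrast significant:** report exactly that, and claim no effect at either visit.

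The cost is a check of existing output and a few reworded sentences, with no new data. The downside is that the stated H4 result may become less favourable.
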